Upon completion of the study, participants will be given the option to receive a report summarising the outcome of the project. In this instance, participants will be asked to agree for researchers to retain their contact details to contact them to disseminate the study findings. Researchers will not access the contact information for those who do not consent to be contacted. All identifiable information will be stored in a password-protected file on a secure computer network and destroyed at the point of dissemination.

Following completion of the study, pseudonymised data will be destroyed after a period of 5 years, in line with Clinical Trial Regulations and to allow for publication of study findings. The Chief Investigator will act as custodian of the data and keep a fully anonymised dataset in a secure location indefinitely.

If a participant wishes to withdraw from the study, the research team will ask how they would like any information provided so far to be dealt with and whether they consent to it still being used in the study analysis.

Compliance

The Chief Investigator will ensure that the trial is conducted in compliance with the principles of the Declaration of Helsinki (1996), and in accordance with all applicable regulatory requirements including but not limited to the UK policy framework for health and social care research, Trust and Research Office policies and procedures and any subsequent amendments.

10. Finance and Publication Policy

Financial considerations

A research budget of up to £1000 is provided for the conduct of this study by the Doctorate in Clinical Psychology at the Institute of Psychiatry, Psychology & Neuroscience, King's College London.

Publication

This project will be disseminated to staff and trainees completing the Doctorate in Clinical Psychology at the Institute of Psychiatry, Psychology & Neuroscience, King's College London. Write-up of the findings will be submitted to the course team as part of a doctoral thesis and will also be submitted to a peer-reviewed journal for publication.

An overall findings report will be provided for participants and participating mental health and maternity services.

The study will be registered on the following public database: www.clinicaltrials.gov

References

Bammens, A. S., Adkins, T., & Badger, J. (2015). Psycho-educational intervention increases reflective functioning in foster and adoptive parents. *Adoption & Fostering*, 39(1), 38-50.

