2.1. Study Objectives

The primary objective of the study is as follows:

- To assess the acceptability and feasibility of a single-session psychoeducational group intervention, Baby CHAT, in women experiencing mild-to-moderate depression during pregnancy

Further, secondary objectives, are:

- To provide preliminary evidence for Baby CHAT's effect on parental RF and prenatal bonding in pregnant women with depression
- To further develop the intervention from participants' feedback and running of the group

The study's primary end point is as follows:

- The study will be completed once Baby CHAT has been run enough times for 24 participants to attend and the last participant has completed their outcome questionnaires 1 month after attending the final group

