2.2 Study Design & Flowchart

Baby CHAT is a novel intervention and, to our knowledge, has never been trialled with pregnant women with depression. Therefore, a feasibility design is appropriate to explore whether Baby CHAT is acceptable to participants, if they experience the intervention as helpful, and to understand whether it is possible to recruit for and complete research on Baby CHAT with this group. Feasibility studies vary in scope but include assessing how practical it is to deliver the intervention, what the demand for the intervention is and how participants respond to it (Bowen et al., 2009). The findings of feasibility studies can then inform subsequent, larger-scale trials on the efficacy of the intervention.

A single-arm repeated measures mixed-methods design will be utilised to provide rich feedback on the acceptability and feasibility of Baby CHAT. The aims of the quantitative arm of the study will be to gather descriptive statistics on the feasibility of the intervention, including uptake and retention of participants and whether the intervention can feasibly be delivered during the given time frame. Effect sizes will also be calculated to inform sample size calculations for a larger-scale clinical trial in the future.

The qualitative arm of the study will gain participants' feedback on the content and impact of the intervention, including their opinions on use of the 4D scan footage, level of adaptation for low mood and any suggested improvements. This qualitative data will provide rich information about participant's experiences of Baby CHAT, that will inform the next stage of the intervention's development.

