Women will be excluded if they are experiencing severe depression or current severe co-morbid diagnoses (e.g. psychosis), if they endorse 'yes, quite often' or 'sometimes' on question ten of the EPDS (in the past 7 days, 'the thought of harming myself has occurred to me'), or if they are unable to complete informed consent and the questionnaires in English. Participants must be able to sufficiently understand the psychoeducational materials and group discussions during the intervention, so that all participants experience a 'high feedback', interactive intervention.

There will be clear signposting to NHS and third sector organisations (including the general practitioner, midwifery team, local psychological therapies service, and other online resources) for all included and excluded participants, given that women interested in the study will be experiencing subjective low mood and may not be accessing treatment.

Withdrawal of subjects

Participants have the right to withdraw from the study at any time for any reason. If participants drop out during the study their data will be included in the analysis, unless they also withdraw consent for this. No further data will be collected from them. Their pseudonymised data will be destroyed after a period of 5 years following completion of the study, consistent with Clinical Trials Regulations and in line with the rest of the data collected in this study. Efforts will be made to report reasons for withdrawal. Withdrawn participants will not be replaced. Withdrawn participants will receive signposting information to local mental health and other support services, as outlined above (see Exclusion criteria).

Statistics

The following quantitative feasibility and acceptability outcomes will be collected: rates of eligible participants, uptake and retention of participants, scores on the feedback form, rates of missing data, and scores on the fidelity checklist (to monitor intervention delivery). For the qualitative arm of the study, participants will complete the open-ended questions on the feedback form. Descriptive data on participant demographic characteristics will also be collected.

The quantitative feasibility and acceptability outcomes outlined above will be summarised descriptively. Qualitative data from the open-ended questions on the feedback form will be analysed using content analysis.

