Although this study is exploratory due to the novelty of the intervention, within feasibility research it is appropriate to set a priori thresholds for the main feasibility and acceptability outcomes. Feasibility thresholds will be as follows: 30 or more potential participants express interest in the study (participant uptake); 20 or more participants attend Baby CHAT (participant retention); and at least 70% of participants complete the study measures (missing data). The acceptability of Baby CHAT will be assessed by the feedback form, which consists mostly of open-ended questions. These will be analysed qualitatively and therefore no specific acceptability thresholds will be set.

Effect sizes for primary and secondary outcome measures will be calculated using Cohen's d. These effect sizes will inform the sample size calculations of future larger-scale studies on Baby CHAT.

Items on the outcome questionnaires will be designated as mandatory on the online survey portal, Qualtrics, to minimise missing data. Participants will be contacted to attempt to complete any missing items from other forms. Therefore, no statistical imputation methods will be required to correct for missing data.

Any deviations from the original statistical analysis plan will be reported in a protocol amendment.

4. Study procedures

Informed consent procedure

All interested participants, whether they self-referred to the study or consented to be contacted via their clinician, will have an initial contact with the research team to ask any questions about the project. Participants will be sent a full Participant Information Sheet by email to read and consider. The information in the Participant Information Sheet and opportunity for further discussion with the research team will allow detailed explanation of the aims, methods, anticipated benefits and potential harms of the study, as well as the participants' right to refuse involvement in the study and to withdraw consent at any time. The research team will ensure adequate time for each participant to consider their consent to take part. Individuals who agree to take part will then be asked to complete and return a signed consent form. All participants will receive a copy of their signed consent form.

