Following informed consent, the depression screening measure (the EPDS) will be conducted. Participants will be informed in a timely and sensitive manner whether they have met the criteria

to be included in the study. Participants who consent but do not score above the threshold on the screening questionnaire will be signposted to appropriate sources of support (as above, see Exclusion criteria).

Study schedule

Following inclusion in the study (i.e. having completed informed consent and scored over the screening threshold), participants will be asked to complete the baseline set of outcome questionnaires via Qualtrics (Time 1). Once completed, the participant will be booked into an upcoming session of the Baby CHAT group.

Participants will attend an online Baby CHAT group at a time that is convenient for them. Up to eight women will be invited to each group, to facilitate optimal group dynamics and engagement with the group content. See below for further details of the intervention.

After attending Baby CHAT, participants will be asked to complete the post-intervention outcome questionnaires and feedback form within 48 hours of the group (Time 2). One month later, participants will be contacted to complete the final follow-up questionnaires (Time 3).

Measures

The primary clinical outcome will be prenatal bonding as measured using the Maternal Antenatal Attachment Scale (MAAS). Secondary clinical outcomes of RF and depressive symptomology will be measured using the Prenatal Parental Reflective Functioning Questionnaire (P-PRFQ) and the Edinburgh Postnatal Depression Scale (EPDS). Feedback forms, containing both qualitative and quantitative components, will also be administered after participants have attended Baby CHAT in order to gather feedback on experience of the intervention (including group format, content and perceived usefulness).

Edinburgh Postnatal Depression Scale

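### If groups run until 24 women attend, the retention threshold of 20 attenders cannot be missed, and the uptake threshold of 30 can be missed only when about 83% or more of interested women attend

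*Combined protocol and SAP*

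**What the plan says.** Section 3 (Statistics) sets three feasibility thresholds in advance:

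- uptake: "30 or more potential participants express interest in the study (participant uptake";
- retention: "20 or more participants attend Baby CHAT (participant retention";
- missing data: "at least 70% of participants complete the study measures (missing data".

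No acceptability threshold is set, so these three are the only pre-set criteria for the primary objective.

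Several places bear on what the planned N=24 counts:

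- Section 2.1, as the primary end point: "The study will be completed once Baby CHAT has been run enough times for 24 participants to attend", with the last woman's 1-month questionnaires complete.
- Section 4 (End of study definition) ties completion to the last group's 1-month follow-up and names no number.
- Section 3 (Withdrawal of subjects): "Withdrawn participants will not be replaced".
- The synopsis gives a study duration of 12 months, and Section 2.2 lists among the aims "whether the intervention can feasibly be delivered during the given time frame".
- Section 4 (Study schedule) places booking after consent, screening and the Time 1 questionnaires: "Once completed, the participant will be booked into an upcoming session of the Baby CHAT group".

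Section 3 also plans to summarise "rates of eligible participants, uptake and retention of participants" descriptively.

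**The concern.** A feasibility threshold is useful only if poor feasibility can make it fail. The number of attenders appears both in the rule that ends the study and in the threshold called retention, and the ending rule asks for more (24) than the threshold does (20). Read as Section 2.1 is written, the retention criterion is settled before any woman is booked. The interest count then works in the wrong direction as a measure of uptake: the worse the conversion from interest to attendance, the more interested women are needed to reach 24 attenders, and the more easily 30 is passed.

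Booked women can fail to attend, because booking comes after enrolment. A report could state that the uptake and retention thresholds were both met when many booked women never came, and Section 2.2 intends the findings to inform larger trials.

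**Working it through.** **Inputs from the documents.** Number attending at the end point: 24 (Section 2.1). Thresholds: 20 attending, 30 interested, 70% completing (Section 3, Statistics). No replacement of withdrawals (Section 3). Duration: 12 months (synopsis). N=24 rests on a recommended range of 24 to 50 and on similar studies of 24 and 25, so there is no sample-size formula to reproduce. The documents give no attendance or conversion rate; every rate and number booked below is an assumption.

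**Reading 1: groups run until 24 attend.** Let A be attenders and I interested women.

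- Retention: A = 24 ≥ 20. The probability of passing is 100% at any attendance rate.
- Uptake fails only if I ≤ 29. Since A = 24 ≤ I, failure means I is 24 to 29, and A/I is then 100%, 96.0%, 92.3%, 88.9%, 85.7% or 82.8%. At I = 30 the ratio is 80.0% and the threshold is met.
- If the last group takes A above 24 the bound rises (25/29 = 86.2%, 26/29 = 89.7%). With 30 or more attenders the threshold cannot fail.
- Assume each interested woman attends independently with probability c, and that interest is counted up to the 24th attender. Then P(I ≤ 29) = P(Binomial(29, c) ≥ 24):

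| Conversion c | P(uptake threshold fails) |
|---|---|
| 50% | 0.03% |
| 60% | 0.8% |
| 70% | 9% |
| 80% | 46% |
| 90% | 94% |

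The better the conversion, the more often the threshold fails.

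**Reading 2: 12 months end recruitment before 24 attend.** Both counts can now fail. With n women booked, each attending with probability p, P(pass retention) = P(Binomial(n, p) ≥ 20):

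| Booked n (assumed) | Attendance p (assumed) | P(pass) |
|---|---|---|
| 30 | 50% | 5% |
| 60 | 50% | 99.7% |
| 20 | 90% | 12% |

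The same 50% attendance nearly always fails or nearly always passes depending on the number booked, and 90% attendance usually fails if few were booked. The count mixes recruitment with attendance.

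**Reading 3: 24 women enrolled, none replaced.** The threshold becomes 20/24 = 83.3%. P(Binomial(24, p) ≥ 20) = 0.111, 0.460, 0.713 and 0.915 at p = 70%, 80%, 85% and 90%. This is a working attendance criterion.

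**Completion threshold.** It can fail on any reading. Of 24, 17 (70.8%) passes and 16 (66.7%) does not, and P(Binomial(24, p) ≥ 17) = 0.032 at p = 50% and 0.192 at p = 60%. Its denominator and time point are not stated: 17 of 24 attenders would be 17/40 = 42.5% of enrolled women if 40 had been enrolled to obtain 24 attenders (assumed).

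**The case against.** The strongest reply is that Section 2.1 states a target, not an open-ended stopping rule. The synopsis gives 12 months, Section 2.2 asks about delivery within the time available, Section 10 caps the budget at £1000, and the poster in Appendix 2 has a removal date of May 2023. A threshold of 20 against a target of 24 makes most sense as an accepted shortfall. Alternatively, inclusion before booking together with no replacement suggests 24 enrolled, in which case 20/24 is a sound criterion. Thirty expressions of interest is a fair measure of demand, which Section 2.2 names as a feasibility question. No go/no-go rule hangs on the thresholds, and the rates will be reported anyway.

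Much of this stands. The by-construction result belongs to Reading 1 only, and the documents do not settle the reading. The interest count is reasonable as a demand measure; the fault lies in calling it uptake and giving it no time window. Sixty bookings, if all were reimbursed at £20, would cost 60 × £20 = £1,200, above the budget, so that row shows the direction rather than a likely scenario.

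Three things do not fall away. Section 2.1 does say attend, and Section 3 ties neither count to a time window. Under a time limit, a count without a denominator still does not measure retention. And descriptive rates do not repair a pre-set criterion labelled retention that can be declared met whatever the rate was.

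**Conclusion.** The concern holds, conditional on the study reaching its stated end point. There the retention threshold is met with certainty, and the uptake threshold can fail only at a conversion of 24/29 (82.8%) or more. These two results are plain arithmetic on the documents' figures and need no assumed rate; the probabilities in the working do rest on assumed rates and independent attendance. If 12 months end first, both counts can fail, but the attendance count still does not measure retention. Only if 24 means enrolled without replacement does 20 act as an attendance criterion.

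This should be fixed, because it affects how the primary objective is judged. It does not endanger the data: the planned rates would still reveal poor attendance.

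**What to change.** Reconcile the synopsis, Section 2.1, Section 3 and the end-of-study definition in Section 4. State whether N=24 counts women enrolled (consented, eligible, Time 1 complete) or women attending, and what happens if 12 months end first. Then, in Section 3:

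1. **Retention.** Define it as attended/enrolled, for example at least 20/24 if 24 are enrolled without replacement. If 24 attenders is kept, use attended/booked with a cut-off that the sponsor fixes in advance, counting a rebooked woman once. Report the exact 95% confidence interval.
2. **Uptake.** Keep 30 expressions of interest as a demand count within a fixed recruitment window. Define uptake as enrolled/interested, or enrolled/screened eligible, with its own cut-off set in advance.
3. **Completion (secondary).** State the denominator and time point of the 70% threshold. All enrolled women at Time 3 is one choice; with 24 enrolled this means at least 17.

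The cost is protocol wording and one log of women interested, screened, enrolled, booked and attended, which the rates already promised largely require. The thresholds could then be failed: 20/24 would be missed 54% of the time at 80% true attendance (1 − 0.460), so the sponsor may prefer a lower cut-off. With 24 enrolled there may be fewer than 24 attenders, and the proportion is imprecise (exact 95% interval for 20/24: 63% to 95%).

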An opportunity sample of participants will be recruited through their clinician or self-referral. This study will recruit participants from South London and Maudsley NHS Foundation Trust (SLaM) who are receiving care within the primary care Improving Access to Psychological Therapies (IAPT) services and secondary care perinatal services in Lambeth, Southwark, Lewisham and Croydon. The student researcher will have no prior relationship with the participants. The research team will share information with clinicians about Baby CHAT and the study procedures, so that they have a good understanding of the study before they are asked to give their patients information about the research. Clinicians will provide eligible clients with a flyer (see Appendix 2 for flyer) and, if a client is interested, will ask for verbal consent for the student researcher to contact them by phone (just name and phone number provided at this stage). To enable self-referral, posters will be placed in the waiting areas of relevant services. Posters will also be placed in maternity scanning clinics at King's College Hospital and St Thomas' Hospital, for participants to self-refer. The study will also be advertised through carefully selected online groups, social media channels and the King's College London research participation email circular.

Once a potential participant has self-referred or consented to be contacted via their clinician, the student researcher will contact them to check eligibility, introduce the project, provide the information sheet and to answer any questions. Participants will have sufficient time to consider whether they consent to take part. Participants will be offered £20 in reimbursement for taking part in the study.

Inclusion criteria

Participants eligible to take part in the project will be women aged ≥ 18 years who are pregnant, between 20- and 34-weeks' gestation, and currently experiencing depressive symptoms as identified by the EPDS. Those scoring >13 will be eligible to take part in the study. Both first-time and experienced parents will be eligible to participate.

Given the study involves the participation of potentially vulnerable individuals, all participants must be resident in or accessing services in a London borough served by SLaM, in order to facilitate access to local mental health services if needed.

Exclusion criteria

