The EPDS (Cox, Holden & Sagovsky, 1987) is a 10-item self-report measure used to identify depression in women during the perinatal period. The scale was initially developed to screen for postnatal depression but has also been validated for use in antenatal populations (Murray & Cox, 1990). Women are asked to rate on a 4-point scale how much they have experienced symptoms over the last week. Total scores are calculated, with higher scores indicating more severe symptoms, and a score of 13 or greater indicating likely depressive illness. The final item on the scale “the thought of harming myself has occurred to me” indicates the presence of thoughts of self-harm or suicide. The EPDS has been shown to have satisfactory sensitivity and specificity (Cox, Holden & Sagovsky, 1987; Gibson et al., 2009).

Maternal Antenatal Attachment Scale

The MAAS (Condon, 1993) is a self-report questionnaire for expectant mothers, designed to assess the maternal-foetal attachment during pregnancy. The scale consists of 19 items on a 5-point Likert scale assessing women’s attitudes, feelings and behaviours towards their foetus. Most items evaluate experiences over the last two weeks, as well as imagined feelings towards the baby when they are born. An overall attachment score is calculated, as well as two subscale scores for ‘quality of attachment’ and ‘time spent in attachment mode (or intensity of preoccupation)’, for example, time spent thinking about the baby. Higher scores indicate stronger maternal-foetal attachment. The MAAS has been shown to have good construct validity (Condon & Corkindale, 1997), internal consistency and split-half reliability (Condon, 1993).

Prenatal Parental Reflective Functioning Questionnaire

The P-PRFQ (Pajulo et al., 2015) is a 14-item self-report questionnaire assessing expectant parents' abilities to think of their foetus as a separate individual with a developing temperament, personality and needs. The scale can be used during the second and third trimester of pregnancy. The 14-item measure asks expectant parents to rate several statements on a 7-point Likert scale, with higher total scores indicating higher prenatal RF. The P-PRFQ has good construct validity and showed strong concurrent validity with an established interview of prenatal parental RF (Pajulo et al., 2015), and therefore shows promising use in both clinical and research settings as a brief, cost-effective measure of prenatal parental RF.

Baby CHAT Feedback Form

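### Must the plan say which Cohen's d it means before the figure can inform a later sample size?

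*Combined protocol and SAP*

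**What the plan says.** Section 3 (Statistics) gives one sentence of analysis for the clinical scales: "Effect sizes for primary and secondary outcome measures will be calculated using Cohen's d". The Study Synopsis repeats it. The purpose is stated twice, in Section 3 ("These effect sizes will inform the sample size calculations of future larger-scale studies on Baby CHAT") and in Section 2.2 ("Effect sizes will also be calculated to inform sample size calculations for a larger-scale clinical trial in the future").

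Section 4 (Measures) makes the MAAS the primary clinical outcome and the P-PRFQ and EPDS secondary. Section 4 (Study schedule) defines Time 1 before the group, Time 2 within 48 hours after it and Time 3 one month later. No section names the pair of times that d compares, the SD used, or an interval. The descriptive commitment in Section 3 is worded for other outcomes: "The quantitative feasibility and acceptability outcomes outlined above will be summarised descriptively".

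For the EPDS, the flowchart in Section 2.3 marks screening, post-intervention and one month, and leaves the baseline cell empty. Section 4 (Screening procedure) agrees on the first of these: "Following informed consent, the depression screening measure (the EPDS) will be conducted". Section 3 (Inclusion criteria) selects on that score: "Those scoring >13 will be eligible to take part in the study". However, Study schedule describes Time 1 as the baseline set of outcome questionnaires without listing them, and the EPDS is one of the outcomes.

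**The concern.** In single-arm pre-post data, Cohen's d has more than one meaning. The mean change can be divided by the SD of the scores or by the SD of the changes. With equal SDs the two agree only when the pre-post correlation is 0.5. A planner given a bare d might enter a change-SD value as a between-group d and plan a trial of the wrong size. A point estimate from about 24 women with no interval would also look firmer than it is.

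The EPDS adds a second worry. If its starting value is the score on which women were selected, some fall on re-measurement is expected without any effect of the session.

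A third is recall. The plan says of the MAAS that "Most items evaluate experiences over the last two weeks", and the EPDS asks about the last week. At Time 2 at least 14 − 2 = 12 of 14 days, and 7 − 2 = 5 of 7 days, precede the group.

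At stake are the secondary objective of preliminary evidence of effect and the inputs to a later trial.

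**Working it through.** **Is there a figure to reproduce?** No. N=24 rests in Section 3 (Sample size) on a recommended range of 24 to 50 and on similar studies. The plan gives no SD, effect size, correlation, alpha or power. Everything below is therefore an illustration on assumptions.

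**1. Choice of SD.** Assume equal SDs at both times, pre-post correlation r, and a raw-SD d of 0.50. Then d(change SD) = d(raw SD) / √(2(1−r)). If that value is mistaken for a between-group d (two-sided alpha 0.05 and 80% power, both assumed), the size per arm is 2 × (1.96 + 0.8416)² / d² = 15.70 / d².

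| r (assumed) | √(2(1−r)) | d on change SD | per arm |
|---|---|---|---|
| 0.3 | 1.183 | 0.42 | 88 |
| 0.5 | 1.000 | 0.50 | 63 |
| 0.7 | 0.775 | 0.65 | 38 |
| 0.8 | 0.632 | 0.79 | 26 |
| 0.9 | 0.447 | 1.12 | 13 |

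The choice of SD can therefore matter if d is reported alone and misread.

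**2. Sampling error.** Inverting the noncentral t with n = 24, an observed change-SD d of 0.50 has a 95% interval of 0.07 to 0.92. Put into the same formula, the unrounded limits imply about 3195 and 19 per arm. The approximate half-widths for d = 0.50 are:

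- change SD, 1.96 × √(1/n + d²/(2n)): 0.42 at n = 24, 0.50 at n = 17, 0.56 at n = 14;
- raw SD at r = 0.7, 1.96 × √(2(1−r)/n + d²/(2n)): 0.34, 0.40 and 0.45.

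Here 17 is 70% of 24 (16.8, rounded up) and 14 is 70% of 20, with the attendance and completion thresholds just met. Even on the raw SD at n = 24, 0.50 ± 0.34 runs from 0.16 to 0.84. That implies 15.70/0.0256, about 610, down to 15.70/0.7056, about 23 per arm. Both spreads are wider than the 88 to 13 in the table.

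**3. Can a reader convert?** Computing any d requires a mean change and an SD. From the SDs at the two times (s₁, s₂) and the SD of change (s_c), the correlation follows: r = (s₁² + s₂² − s_c²) / (2s₁s₂). All three come from data already scheduled in the flowchart. Conversion fails only if the report gives d and nothing else, and the plan does not say it will.

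**4. EPDS.** Assume an unselected EPDS with mean 8 to 12 and SD 5, a cut at 13.5 and a retest correlation of 0.6 to 0.9. With a = (13.5 − mean)/5 and λ = φ(a)/(1 − Φ(a)), the expected fall is 5λ(1−r) and the selected SD is 5√(1 + aλ − λ²).

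- Mean 8, r = 0.6: a = 1.1, λ = 1.606, fall 3.21 points, selected SD 2.17, d = 1.48.
- Mean 12, r = 0.9: a = 0.3, λ = 0.998, fall 0.50 points, selected SD 2.75, d = 0.18.

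Selection alone could thus produce a d of about 0.2 to 1.5. Dividing by the pre-session SD does not cure this: if that is the screening score, its SD is itself narrowed by the cut, which enlarges d.

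**5. What depends on d?** The thresholds in Section 3 are 30 or more expressing interest, 20 or more attending and at least 70% completing the measures. None uses d. No test, stopping rule or progression decision rests on it.

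**The case for a change.** The strongest case for changing the plan is that it sets this purpose for d itself, and that a few sentences on contrast, SD and interval would cost nothing in data or burden. Without them the choice can be made after the results are seen. The undertaking in Section 3 to report deviations from the analysis plan would not catch it, because there is nothing stated to deviate from. The descriptive summary is also worded for feasibility and acceptability outcomes, so means and SDs of the scales are not expressly promised.

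The gap itself stands: no other section fills it. The consequence does not follow. With three fixed times, the natural contrasts are from the pre-session value to Time 2 and to Time 3. Two contrasts on three scales make six effect sizes, few enough to report in full. Nothing is decided on any of them, so a favourable choice gains little.

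On the EPDS, the flowchart and the Time 1 wording can be read differently, but a pre-session score exists on either reading. The fall on re-measurement limits what any uncontrolled change from a selected score can show. The recall overlap concerns when Time 2 falls, not how d is defined. Its effect cannot be sized from the documents, and Time 3, a month on, lies clear of it.

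**Conclusion.** No change to the plan is needed. The missing contrast, SD and interval are details that an analyst of a small feasibility study fills in the ordinary course by reporting means, SDs and numbers alongside d. No stated rule or figure is wrong, and the feasibility thresholds and N=24 are untouched.

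On assumed correlations of 0.3 to 0.9, the choice of SD turns a d of 0.50 into 0.42 to 1.12, or 88 to 13 per arm if misused. Sampling error at 24 women spans 0.07 to 0.92, or about 3195 to 19 per arm. Fixing the SD would therefore leave most of the uncertainty in place. It would also not make an uncontrolled pre-post change, at Time 2 or Time 3, into a between-group effect.

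The EPDS change needs the usual caution about selection when results are read. The conclusion rests on the report giving more than a bare d. The correlations, EPDS distribution, alpha and power used here are assumptions, since the documents give none.
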